In this study we will use a randomized controlled trial to assess the impact of a 6-month long intervention of empathetic relationship building engagement with emotional and motivational support delivered telephonically for patients with diabetes at a Federally Qualified Health Center (FQHC). Telephone callers, lay people with light training on how to be empathetic and engaging in calls, will support participants' journeys on their own goals related to nutrition, exercise, sleep and medication adherence. They will not provide diabetes specific information, instead they will support people walking more, sleeping better, eating better and taking their medications. The impact of the program will be assessed primarily on Hemoglobin A1C levels and secondarily on depression and mental health at the end of the 6-month intervention, and in the following 6 months. Results will be compared to patients in the control arm that receive usual care. Participants will be recruited from our partner, an FQHC, Lone Star Circle of Care (LSCC) and include patients with Hemoglobin A1C of greater than 8.0 as measured at any point in the 12 months preceding enrollment.

- Chaoyang Li, Earl S. Ford, Tara W. Strine, Ali H. Mokdad. Prevalence of Depression Among U.S. Adults With Diabetes Diabetes Care Jan 2008, 31 (1) 105-107; DOI: 10.2337/dc07-1154
- Kahlon MK, Aksan N, Aubrey R, et al. Effect of Layperson-Delivered, Empathy-Focused Program of Telephone Calls on Loneliness, Depression, and Anxiety Among Adults During the COVID-19

Pandemic: A Randomized Clinical Trial. JAMA Psychiatry. 2021;78(6):616–622. doi:10.1001/jamapsychiatry.2021.0113

- Impact of a Telephonic Intervention to Improve Diabetes Control on Health Care Utilization and Cost for Adults in South Bronx, New York
- Bahman P. Tabaei, Renata E. Howland, Jeffrey S. Gonzalez, Shadi Chamany, Elizabeth A. Walker, Clyde B. Schechter, Winfred Y. Wu Impact of a Telephonic Intervention to Improve Diabetes Control on Health Care Utilization and Cost for Adults in South Bronx, New York. Diabetes Care Apr 2020, 43 (4) 743-750; DOI: 10.2337/dc19-0954

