#### To input text, click in the light grey area below.

Our primary outcome of interest is Hemoglobin A1C. However, the approach being used is modeled after a successful mental health intervention (Kahlon et al 2021) which showed depression can be improved with the type of empathy calls utilized in the current study.

To ensure that the effect of the empathy calls program on A1c can be assessed without confounding it with depressive mood in the first 6-month phase-I portion, we will rely on stratified randomization so that

approximately 50% (N=75) of the individuals in both the control and experimental group have a PHQ9  $\geq$ 5 at baseline and 50% of the individuals have PHQ9 <5 at baseline. With 150 individuals in each arm, three assessments for A1c, the primary outcome, and depression (PHQ9), secondary outcome, we have 80% statistical power with alpha = .05 to detect effects as small as f = .09, which is a small, standardized effect size, and have 90% power to detect effects as small as f = .10, also a small effect size, assuming only a moderate correlation for rank-order stability across time for each outcome of r = .30. This correlation is reasonable for A1c and is an underestimate for the typical correlation for PHQ9. Statistical power for the effect of interest increases as these correlations in the outcome measures goes up. Regarding correlations, we have 90% power to detect correlations as small as r = .26 and 80% power to detect correlations as small as r = .23 within each group (N = 150) at alpha = .05. These are fair to moderate effect sizes that bear on the power of any follow-up mediation analyses.

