We will test differences in the trajectory of A1c over the course of six-months with three assessments (baseline, 3- and 6-months) for those who receive empathy calls to support diabetes self-management versus those who do not receive these support calls. We will rely on linear mixed effect regressions with random terms to model individual differences in both the intercept and change terms, accounting for the clustering effect of shared lightly trained callers. We will predict these trajectories using the following person-level covariates: grouping indicator, terms to capture diabetic treatment type and dose, change in PHQ9 from baseline to 6-month depression. The cross-level interaction of grouping indicator with time will constitute the effect of interest. In addition, if change in depression predicts the person-specific slopes for A1c and does so more strongly for those in the intervention than control group, we would have evidence that depression management affects A1c course. Similar models will be constructed for the secondary outcome of depression, PHQ9 across three waves of data collection, with frequency/duration of support calls across those waves modeled as a time-varying covariate. Person-level covariates will include grouping indicator, terms to capture change in A1c from baseline to 6-months. If change in A1c predicts person-specific slopes for depression and does so more strongly for those in the intervention than control, we would have preliminary evidence that improved control of A1c affects course of depression, an unlikely outcome. The outcome of these mixed effect regressions will permit a preliminary estimate of the mediational role of depression on A1c management in phase-I. We will estimate those indirect effects using bootstrapped standard errors using the MPlus modeling framework for longitudinal change from baseline to 6-months. Healthcare utilization outcomes both self-reported and obtained from LSCC will be harmonized into a composite score of utilization. Depending on the distribution of each aspect of utilization (ER visits, hospitalization, PCP visits), we will construct models to predict differences between the intervention and control arm while covarying change in A1c and depression from baseline to 12-months.

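### The only stated A1c model for phase I adjusts for 0–6 month PHQ-9 change, a mediator by the plan's own account, so arm x time need not be the total randomised effect

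*Combined protocol and SAP*

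**What the plan says.** The combined protocol and SAP sets the question in section 2 (Research Hypothesis): "The impact of the program will be assessed primarily on Hemoglobin A1C levels", with usual care as the comparator.

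Section 5 (Data Analysis) describes a linear mixed model for A1c at baseline, 3 and 6 months, with random intercepts and slopes and an allowance for shared callers. It then lists the predictors: "We will predict these trajectories using the following person-level covariates: grouping indicator, terms to capture diabetic treatment type and dose". The list ends with PHQ-9 change, and the next sentence names the target effect: "change in PHQ9 from baseline to 6-month depression. The cross-level interaction of grouping indicator with time will constitute the effect of interest".

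The following sentence asks a further question of the model: "if change in depression predicts the person-specific slopes for A1c and does so more strongly for those in the intervention than control group".

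Two other statements in section 5 define the role of depression. The earlier trial of the approach "showed depression can be improved with the type of empathy calls utilized in the current study". The regressions are also meant to "permit a preliminary estimate of the mediational role of depression on A1c management in phase-I".

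No A1c model without PHQ-9 change appears in section 2, 4, 5 or 15.

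**The concern.** PHQ-9 change from 0 to 6 months is measured over the same period as the outcome. The plan expects the calls to alter it, and expects it in turn to affect A1c. Conditioning on it in the model that supplies the primary contrast raises three problems.

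- **Different quantity.** If PHQ-9 change acts on slopes, arm x time compares the arms at equal mood change. Benefit that reaches A1c through mood is removed, although this is the pathway the programme is built on.
- **Lost protection.** The conditional contrast is open to confounding by common causes of mood change and A1c change. Randomisation does not balance these within levels of a post-randomisation variable.
- **Undefined result.** If the comparison of arms on the PHQ-9 slope sits in the same model (arm x PHQ-9 change x time), arm x time also depends on how PHQ-9 change is centred, which is not stated.

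If mood and A1c improve together, a working programme is more likely to be missed, and a reader could not tell which effect had been reported.

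**Working it through.** **1. The plan's own power figure.** Inputs from section 5: 300 participants, 3 assessments, r = .30, alpha .05. For the group x time test in a repeated-measures ANOVA, lambda = f² x 300 x 3 / (1 − .30), with 2 and 596 df. The smallest detectable f is .0868 at 80% power and .0995 at 90%, which round to the stated .09 and .10. The between-group version gives only 57% and 66% power at f = .09 and .10. The stated power is therefore for group x time, with no PHQ-9 term in the formula.

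**2. Does the form of entry matter?** One large simulated data set (1,500 per arm, complete data, total effect −0.5 A1c points, half mediated) was fitted with random intercepts and slopes:

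| PHQ-9 change enters as | arm x time |
|---|---|
| not included | −0.479 |
| main effect only | −0.479 |
| x time | −0.197 |
| x time and x arm | −0.206 |

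Main-effect entry is harmless with complete balanced data. Slope entry is not. The text supports slope entry, because the covariates are said to predict trajectories and PHQ-9 change is asked to predict person-specific slopes.

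**3. Size under slope entry.** Two inputs are not in the documents and are varied: rho, the within-arm correlation of PHQ-9 improvement with A1c improvement, and dM, the programme's effect on PHQ-9 change in change-SD units. The plan gives "80% power to detect correlations as small as r = .23 within each group (N = 150", but that is a detectable value, not an expected one. By design, "50% of the individuals have PHQ9 <5 at baseline"; these participants have little room to improve, so dM may be small.

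- SD of A1c change = sqrt(2 x (1 − .30)) = 1.183 SD.
- Effect with 80% power for baseline-to-6-month change at 150 per arm (two-sided .05, t test, 298 df) = 0.3245 change-SD; 0.3245 x 1.183 = 0.384 SD.
- Adjusted estimate = (0.3245 − rho x dM) x 1.183.
- SE in change-SD = sqrt(1 − rho²) x sqrt(2/150) x sqrt(1 + dM²/4); power from the noncentral t, 297 df.

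Example, rho .23 and dM 0.4: (0.3245 − 0.092) x 1.183 = 0.275 SD; share removed 0.092/0.3245 = 28%.

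| rho | dM | share removed | estimate (SD) | power |
|---|---|---|---|---|
| .10 | 0.1 | 3% | 0.372 | 78% |
| .10 | 0.2 | 6% | 0.360 | 75% |
| .10 | 0.4 | 12% | 0.337 | 68% |
| .23 | 0.1 | 7% | 0.357 | 76% |
| .23 | 0.2 | 14% | 0.330 | 69% |
| .23 | 0.4 | 28% | 0.275 | 52% |
| .26 | 0.4 | 32% | 0.261 | 49% |
| .26 | 0.6 | 48% | 0.199 | 30% |

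If rho or dM is zero, nothing is removed. If rho is −.10 with dM 0.4, the estimate rises to 0.431 SD. Simulation of 4,000 runs at rho .23, dM 0.4 gave 0.274 SD and 52% power. Caller clustering is not modelled.

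**4. Zero total effect.** The adjusted contrast is then −rho x dM. With dM 0.4 and rho .23/.26, rejection is 12.3%/14.7% against the programme and 0.3%/0.2% in its favour, against a nominal 2.5% each side. At rho .10, dM 0.2, total rejection is 5.3%. False findings of benefit become more frequent only if rho is negative (5.3% in that tail at rho −.10, dM 0.4).

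**5. Centring.** With an arm-specific PHQ-9 slope (assumed rho .36 intervention, .10 control, dM 0.4), arm x time is:
- (0.3245 − .36 x 0.2 − .10 x 0.2) x 1.183 = 0.275 SD if grand-mean centred;
- (0.3245 − .36 x 0.4) x 1.183 = 0.214 SD at zero PHQ-9 change;
- (0.3245 − .36 x 0.7 + .10 x 0.3) x 1.183 = 0.121 SD at zero PHQ-9 change, if controls also improve by 0.3.

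**6. Separate check by mediated share.** 400 simulated trials per row, 150 per arm. Assumed: total effect −0.5 A1c points, programme lowers PHQ-9 by 2 points, SD of PHQ-9 change 4.5, and no mediator–outcome confounding.

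| share mediated | arm x time without / with PHQ-9 slope | power without / with |
|---|---|---|
| 0% | −0.51 / −0.51 | 0.91 / 0.90 |
| 10% | −0.50 / −0.45 | 0.93 / 0.85 |
| 25% | −0.51 / −0.39 | 0.87 / 0.66 |
| 50% | −0.50 / −0.25 | 0.85 / 0.36 |

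**The case against.** **The damage depends on one reading.** The interaction with time is attached to the grouping indicator alone, the slope question opens as an addition, and section 5 refers to regressions in the plural and to follow-up mediation analyses. PHQ-9 change could therefore enter as a main effect or in a second model. This stands as a limit on certainty. It does not rescue the plan: the covariate is listed in the same model from which the effect of interest is taken, and no model without it is named. The Mplus step is described only as estimating indirect effects.

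**The size is assumed.** This stands. The larger losses need dM near 0.4 and correlations that the plan gives only as detectable. At rho .10 and dM 0.1 to 0.2 the loss is 3% to 6%.

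**The starting effect is not the plan's f = .09.** This also stands. Under linear divergence over three visits, f = d/sqrt(24), so d = .09 x 4.899 = 0.44 SD. In the formula above, unadjusted power is then about 90%. It falls to about 68% at rho .23, dM 0.4 (25% removed) and to about 82% at rho .23, dM 0.2. The illustrative powers change; the estimand problem does not.

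**The error-rate result is conditional.** Correct. It needs non-zero rho and dM. With zero total effect, either rho comes from common causes of mood and A1c, or a real mood benefit is exactly offset by a harmful direct effect.

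**Conclusion.** The concern holds. Followed as the text best reads, the primary A1c test estimates a programme effect conditional on mood change, not the total effect versus usual care. The two coincide only if the calls do not shift PHQ-9 or PHQ-9 change is unrelated to A1c slope, which runs against the plan's rationale.

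The size cannot be fixed from the documents. Over the positive correlations examined it runs from nothing to about half the effect (48% at rho .26, dM 0.6), and a negative correlation would inflate the estimate instead. Any distortion of the error rate under positive correlation is almost entirely towards a false finding against the programme. These figures assume slope entry, complete data and a common within-arm correlation (except in the centring example).

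The case for change does not rest on the size: the meaning of the primary result should not depend on an unstated coding choice.

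**What to change.** In section 5, remove 0–6 month PHQ-9 change from the primary A1c model and state the model in full, for example:

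> The primary effect is arm x time from a mixed model of A1c at 0, 3 and 6 months on arm, time, arm x time, baseline PHQ-9 stratum (>=5 / <5), and treatment type and dose as recorded at baseline, with the planned random terms and caller clustering, including all randomised participants in their assigned arm.

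The essential change is the removal of PHQ-9 change. The baseline stratum reflects the stratified randomisation. Specifying baseline treatment matters because the measures table in section 4 collects medication at every visit, and later values would be another post-randomisation covariate.

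Keep PHQ-9 change only in the mediation analysis already planned, labelled exploratory. The cost is a wording change, with no new data, visits or participants.

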**Measure Collection:** Biomedical measures will be directly collected in person at their clinic site, Dell Medical School at The University of Texas at Austin, or a community site that is convenient (A1C and Blood pressure). Patient-reported measures will be collected through self-report on a tablet (or paper copy if participant chooses) at the same time biomedical measures are collected. Electronic Health Record measures will be collected via a data agreement with Lone Star Circle of Care (LSCC).

Measure	Freq	ΤοοΙ	
Program Effects			
Hemoglobin A1C	Baseline/3 mths/6 mths/9 mths/12mths	Finger stick on portable device	

Blood Pressure	Baseline/3 mths/6 mths/9 mths/12mths	Automatic blood pressure cuff
Depression	Baseline/3 mths/6 mths/9mths/12 mths	PHQ-9
Anxiety	Baseline/3 mths/6 mths/9 mths/12 mths	GAD-7
General Health	Baseline/3 mths/6 mths/9 mths/12 mths	SF-12
Healthcare Utilization (PCP & BH clinic, Hosp, ED visits)	Baseline/3 mths/6 mths/9 mths/12 mths	Customized (4 new questions added)
Healthcare Utilization (PCP visits, BH visits)	Data pulls for data collected during program	LSCC ElecHealthRecord
Medication Related to DM and HTN	Baseline/3 mths/6 mths/9 mths/12mths	Customized
Medication Adherence Survey	Baseline/3 mths/6 mths/9 mths12 mths	Med Adherence Report Scale (MARS 5)
Diabetes Self-Management	Baseline/3 mths/6 mths/9 mths/12 mths	Perceived Diabetes Self- Management Scale (PDSMS)
Diabetes Self Care	Baseline/3 mths/6 mths/9 mths/12 mths	Summary of Diabetes Self-Care Activities (SDSCA)
Diabetes Self Efficacy	Baseline/3 mths/6 mths/9 mths/12 mths	Stanford Self-Efficacy for Diabetes Scale
Diabetes Distress	Baseline/3 mths/6 mths/9 mths/12 mths	Diabetes Distress Screening Scale
Loneliness	Baseline/3 mths/6 mths/9 mths/12 mths	UCLA 3-item Loneliness Scale
Onset Date of Diabetes	Baseline	Customized
Social Needs Survey	Baseline/6 mths/12 mths	Adapted from PRAPARE
Social Support	Baseline	Lubben Social Network scale
Participant Demographics	Baseline	Customized
Household demographics	Baseline	Customized
Interest in Calling Others	6 mths	Customized
Program Satisfaction	6 mths (intervention arm only)	Customized
Program Improvement	12 mths (intervention arm only)	Customized
Program Implementation		
Call Occurrence	Continuous (daily; did it happen)	Twilio report
Call Connection	Continuous (daily; did the call connect to a person)	Twilio report
Call Duration	Continuous (daily); for every call placed, duration	Twilio report

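### The A1c, PHQ-9 and utilisation arm comparisons each adjust for a change score that needs the closing visit, and with no stated handling of missing covariates a standard fit drops participants who miss it

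*Combined protocol and SAP*

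**What the plan says.** All three models are in Section 5 (Data Analysis).

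- **A1c (primary).** The method is "linear mixed effect regressions with random terms to model individual differences in both the intercept and change terms", fitted to baseline, month 3 and month 6. The person-level covariates include "change in PHQ9 from baseline to 6-month depression". In the same model, "The cross-level interaction of grouping indicator with time will constitute the effect of interest". The change score therefore sits in the primary comparison itself, not only in a later mediation step.
- **PHQ-9 (secondary).** "Person-level covariates will include grouping indicator, terms to capture change in A1c from baseline to 6-months".
- **Healthcare utilisation.** Self-report and clinic records are to be combined into a composite, and the arms compared "while covarying change in A1c and depression from baseline to 12-months".

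Under Measure Collection in Section 4, surveys (including PHQ-9) are completed at the visit where A1c is taken. The measures table lists two sources for utilisation. One is a survey at study visits, which covers primary care, behavioural health, hospital and emergency visits. The other is the clinic's electronic record, covering primary care and behavioural health visits only, with timing given as "Data pulls for data collected during program".

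The plan states no analysis population, no missing-data method, and no version of these three models without the change score. Mplus is named only for the indirect effects. The mediation analysis and the Phase 2 comparisons state no such covariate.

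**The concern.** A likelihood-based mixed model can use a participant who has baseline and month-3 A1c but misses month 6. It has no such tolerance for a missing covariate: as ordinarily fitted, every row with a missing covariate is left out. Because A1c and PHQ-9 come from the same visit, one missed month-6 visit leaves both change scores undefined and removes all of that person's rows from both models.

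The primary comparison would then be restricted to people selected on attendance after randomisation. Two things are at stake: precision, and the protection a mixed model gives when drop-out depends on the observed month-3 result. This is separate from whether a possible mediator should be adjusted for. It concerns who can be analysed, and would remain even if the adjustment were accepted in principle.

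**Working it through.** **Inputs from the documents.** 150 per arm, 300 in total, three assessments, r = .30 across time, alpha .05 (Sections 5 and 15). **Assumed, because the documents do not give them:** closing-visit loss of about 10-30%, A1c SD, drop-out mechanism, and a true effect of 0 or -0.6 A1c points.

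1. **The plan's own figure.** For a repeated-measures group-by-time F test, lambda = f² × N × m / (1 - r), with 2 and 596 degrees of freedom.
   - f = .09: lambda = .0081 × 300 × 3 / .70 = 10.41, power 83.0%. The detectable f at 80% power is .0868, which rounds to .09.
   - f = .10: lambda = .01 × 900 / .70 = 12.86, power 90.3%. The detectable f at 90% power is .0995.
   - The stated figures reproduce. They assume all 300 are analysed, with no allowance for loss.

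2. **People and values lost if rows with a missing covariate are dropped.** With a fraction d missing month 6 but seen at month 3, n = 300(1 - d). Collected A1c values discarded = 2(300 - n), out of 900 - (300 - n).

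| Missing month 6 | People analysed | A1c values discarded | Power at f = .09 |
|---|---|---|---|
| 5% | 285 | 30 of 885 | 80.9% |
| 10% | 270 | 60 of 870 | 78.6% |
| 20% | 240 | 120 of 840 | 73.3% |
| 30% | 210 | 180 of 810 | 67.1% |

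   The fall in power overstates what the covariate costs, because some information is lost with the missed visit under any analysis. Step 4 isolates the covariate's share.

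3. **Direct check.** In one simulated data set with 62 of 300 people missing month 6, a mixed model without the change score used 300 people and 838 rows. With it, and rows with missing covariates removed, 238 people and 714 rows remained: 838 - 714 = 124 measured values lost, or 2 × 62.

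4. **Precision when drop-out is unrelated to outcome or acts alike in both arms.**
   - Compound symmetry, SD 1.5, r = .30 or .60, losses of about 11-28%: completers-only bias 0.02 or less, SE 1-6% larger than with all available data, power up to 6 points lower.
   - Random-slope covariance (SD about 1.3 to 1.7), drop-out completely at random: SE .211 against .207 at 10% loss (2% larger), .224 against .214 at 20% (5%), .239 against .222 at 30% (8%).

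5. **Bias when drop-out depends on month-3 change in one arm only.**
   - Compound symmetry, SD 1.5, about 21% loss, log-odds 0.7 per SD of 0-3 month change, poor responders leaving the control arm. At r = .30, completers-only bias is +0.13, type I error about 9%, and power about 55% for a true -0.6. All available data give bias of at most 0.01, type I error about 5% and power about 78%. At r = .60, bias is about +0.10, type I error about 9%, and power about 82% against 95%.
   - Same setting, r = .30, poor responders leaving the intervention arm: bias about -0.12, in favour of the intervention.
   - Random-slope covariance, intervention-arm drop-out, no true effect: completers-only bias -0.20, -0.30 and -0.38 at nominal losses of 10%, 20% and 30%, with type I error 15.5%, 25.9% and 33.6%. All available data: bias within 0.01, type I error 5.1-5.6%.

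   These runs compare all available data with completers. They contain no PHQ-9 covariate and no caller clustering, so they stand in for the planned model rather than reproduce it.

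6. **Utilisation.** For clinic-record counts, losing a fraction d of participants multiplies the SE by 1/√(1 - d): 1/√.90 = 1.05 and 1/√.70 = 1.20, so 5-20% larger for 10-30% loss. This applies to primary care and behavioural health visits only. Emergency and hospital visits, and the composite, also need self-report at study visits.

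**The case against.** The strongest reply is that the plan nowhere prescribes complete-case analysis. Exclusion follows from ordinary software behaviour when nothing else is specified. Multiple imputation, or treating the change score as a modelled variable under full-information likelihood, would keep these participants. The phrase "terms to capture change in A1c from baseline to 6-months" could even be read as model-estimated change. This stands as a condition on the point. It does not remove it: no such method is written down, and the named covariate is what makes the omission costly in a model otherwise able to use partial data.

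Second, the bias figures need drop-out that depends on month-3 response differently by arm. The arms do receive very different contact in the first six months, so differing attendance is plausible, but the documents offer no evidence for any particular pattern, SD or effect. A reader might infer that the primary result will be biased towards no effect. The documents do not support that, since the sign follows from which arm loses its poor responders.

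Third, a reader might take clinic records to rescue the whole utilisation analysis. They cannot, because emergency and hospital visits are collected only by survey.

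Finally, removing the change score is also what an objection to adjusting for a mediator would ask for. The remedies overlap, but the reasons are distinct.

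**Conclusion.** The point holds for the A1c, PHQ-9 and utilisation arm comparisons, on the condition that missing covariates are handled in the ordinary way, since no alternative is stated. It does not extend to every analysis in Section 5. That participants and their measured month-3 values are lost follows from the specification and that handling. How many are lost, and whether bias results, rests on assumptions.

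At 10-30% loss the likely minimum cost is a modest loss of precision. Material bias requires drop-out related to early response differently by arm. It is then about 0.1 A1c points either way, with type I error about 9% at 21% loss under compound symmetry, and larger with random slopes. It would go too far to say that the plan mandates a completers-only analysis or that its result must be biased. What can be said is that, as written, it gives up the main advantage of its chosen model and states nothing to restore it.

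**What to change.** 1. Estimate the A1c and PHQ-9 group-by-time effects in mixed models without the end-of-follow-up change score, using every randomised participant with any available outcome.
2. Compare utilisation between arms without the 12-month change scores. Use all participants with clinic records for primary care and behavioural health visits, and all available self-report waves for emergency visits and hospitalisation. State how the composite is formed when a wave is missing.
3. Address the depression-A1c question separately, in a joint (parallel-process) growth model of A1c and PHQ-9 under full-information maximum likelihood in Mplus, which the plan already names. Participants with only baseline and month-3 data then contribute.

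The cost is analysis-plan wording and slightly more modelling. No new data are needed, and the mediation aim is kept.

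### The rule for concluding that depression management affects A1c rests on concurrent 0-6 month changes and cannot show direction; mediation should rest on the planned indirect effect, labelled exploratory

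*Combined protocol and SAP*

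**What the plan says.** Section 5 models A1c at baseline, 3 and 6 months with random intercepts and slopes. Among the person-level covariates is "change in PHQ9 from baseline to 6-month depression". The forward rule reads: "if change in depression predicts the person-specific slopes for A1c and does so more strongly for those in the intervention than control group", then "we would have evidence that depression management affects A1c course".

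The roles are then swapped: "Similar models will be constructed for the secondary outcome of depression, PHQ9 across three waves of data collection", with person-level covariates that include "terms to capture change in A1c from baseline to 6-months". The mirror rule reads: "If change in A1c predicts person-specific slopes for depression and does so more strongly for those in the intervention than control", then "we would have preliminary evidence that improved control of A1c affects course of depression, an unlikely outcome".

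The same section says that these regressions will permit a preliminary estimate of mediation by depression. Indirect effects with bootstrapped standard errors are to be estimated for change from baseline to 6 months. It gives no rule for the case where both conditions are met, no lagged model, and no assumption about confounding between mood change and A1c change. The measures table in Section 4 shows that PHQ-9 and A1c are both collected at 3 months.

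**The concern.** Predictor and outcome span the same six months in both rules, so neither precedes the other. Yet one result is to be read as an effect of mood on A1c, and its mirror as an effect of A1c on mood that the plan already calls unlikely. Randomisation protects the comparison of arms. It does not protect the relation between two changes that both arise after randomisation, and neither does stratifying on baseline PHQ-9.

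The criterion also asks a different question from mediation. A stronger slope in one arm is moderation. If the calls improve mood, and mood acts on A1c in the same way in everyone, depression mediates the effect and the criterion is still not met.

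The study hypothesis (Section 2) is a mental-health-first approach, so a claim that mood management drives A1c would be a leading interpretation of the trial. The rule could support that claim when it is false and withhold it when it is true.

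**Working it through.** **The plan's own figures.** For mediation, Section 5 quotes detectable within-group correlations of .23 (80% power) and .26 (90%) with N = 150. By Fisher's z, two-sided .05, power = Φ(atanh(r)·√147 − 1.96). For r = .23: .2342 × 12.124 − 1.96 = .88, power .810. For r = .26: .2661 × 12.124 − 1.96 = 1.27, power .897. Both reproduce. They concern one correlation against zero, whereas the rule compares two arms. The smallest difference in Fisher's z detectable with 80% power is (1.96 + .842) × √(2/147) = .327.

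**Step 1: the slope is the change.** At months 0, 3 and 6 the deviations from the mean time are −3, 0, 3, with sum of squares 18. The least-squares weights are −3/18, 0, 3/18, so slope = (month 6 − month 0)/6. The forward rule regresses A1c change on PHQ-9 change, and the reverse rule does the opposite. One simulated data set fitted by mixed model agreed. The cross-level coefficients equalled those from regressing (month 6 − month 0)/6 on the other change: .00450 and .01451 forward, .03044 and .10219 reverse. Standard errors need not agree: the reverse arm interaction had t = 1.57 in the mixed model and 2.06 in the simple regression.

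**Step 2: what is identical and what is not.** The pooled predictor test, given arm, depends only on the partial correlation of the two changes, which is symmetric. Across simulated trials the two directions gave the same t (largest difference about 1e-14). The arm-by-predictor tests are not identical, because each slope also depends on the arm's variances.

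**Step 3: how often the rules are met.** Assumed, because the documents give no values: standardised changes, no missing data, no further covariates. Both conditions were applied (pooled predictor t > 1.96 and arm interaction t > 1.96, 150 per arm).

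| True structure | Forward, correlations .10/.40 | Forward / reverse / both, correlations .15/.55 |
|---|---|---|
| Depression drives A1c | 76-77% | .965 / .964 / .944 |
| A1c drives depression | 76-77% | .959 / .960 / .936 |
| Common cause only | 76-77% | .965 / .963 / .941 |

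At .10/.40 the reverse rule was met about equally often. The interaction t statistics correlated at about .86, and exactly one rule was met in about 12% of trials. At .15/.55 the t statistics correlated .72-.75.

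Hand check at .10/.40: (.4236 − .1003)/√(2/147) = .3233/.1166 = 2.77, and Φ(2.77 − 1.96) = .79. This is close to the simulation and symmetric in the two variables. The gap of .323 is almost the .327 that the design can just detect.

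**Step 4: ordinary mediation.** With an equal path of .35 (assumed) in both arms, the forward rule was met in .028 of trials. The expected value is near .025, one tail of a two-sided 5% test, because the true slope difference is zero.

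**Step 5: the planned indirect effect.** A joint-significance proxy for the bootstrap (assumed arm effect 0.3 SD, correlations .15/.55) was positive in .746 of trials with real mediation, .741 with a common cause only, and .294 when A1c drove depression. It detects mediation but does not separate it from confounding.

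**The case against.** The plan is partly protected, and four stronger readings should be resisted.

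- **That the plan misses ordinary mediation.** A reader might infer this from the 3% figure. The documents do not support it: Section 5 also plans bootstrapped indirect effects, which need no stronger slope in the intervention arm. Only the stated rule misses equal-slope mediation.
- **That the two rules are one test and are always met together.** They are not. The interaction tests differ in about 12% of trials even with equal variances. With a common cause only and a 1.3-fold larger SD of PHQ-9 change in the intervention arm, the rules were met .816 (forward) and .996 (reverse) of the time. The planned covariates also differ: treatment type and dose in the A1c model, call frequency and duration in the PHQ-9 model. This does not rescue the inference, since such a split reflects variances or covariates and not direction.
- **That the primary result is compromised.** Section 5 names the arm-by-time interaction as the effect of interest and introduces the depression rule as an addition. The mediation estimate and the reverse conclusion are called preliminary. The forward conclusion carries no such qualifier.
- **That a lagged model should replace the planned one.** Adjusting 6-month A1c for 3-month A1c removes any mood effect already present by month 3. Calls are most frequent in the first month, so early effects are plausible. In an assumed scenario where mood acts on A1c within the same three-month window, joint-significance power was about .03 for such a model, against .97 for 0-6 month change. Lagging also leaves a persistent common cause in place.

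What stands of the objection is that this concerns the wording and criterion of a secondary mechanism analysis.

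**Conclusion.** The concern holds in limited form. The stated rule cannot support a directional conclusion. It is met about equally often (76-77% at assumed within-arm correlations of .10 and .40, about 96% at .15 and .55) under depression driving A1c, the reverse, or a common cause. As a criterion for mediation it is met only about 3% of the time when the path is equal in both arms.

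The slope identity is algebra for complete data at 0, 3 and 6 months. The percentages depend on the assumed correlations, equal variances within arms and no extra covariates. The similarity across causal structures appeared at both sets of correlations tried. The planned indirect effect remains usable for ordinary mediation, provided that its confounding assumption is stated.

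**What to change.** In Section 5, before the data are analysed:

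1. Delete the requirement of a stronger association in the intervention arm as the criterion for a depression effect. If the arm difference in slopes is of interest, report it as moderation.
2. Describe both change-on-change results as associations without direction, and remove the two causal conclusions.
3. Base the mediation statement on the already planned bootstrapped indirect effect of randomised arm through PHQ-9 change, and label it exploratory.
4. State the assumption of no unmeasured mediator-outcome confounding, and add a sensitivity analysis showing how strong such confounding would have to be to remove the indirect effect.
5. Optionally, add a time-ordered model using the 3-month visit, with its mirror, as a supplement and not a replacement, for the reasons given under the objection.

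The cost is revised wording and a modest amount of extra analysis. No new visits, measures or participants are needed. The downside is a more modest mechanism claim.
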